9.3. Informed Consent

Informed consent will be sought by delegated ABUHB research delivery team members named on the delegation log. Eligible participants will be provided with verbal information about the study and given a copy of the written Patient Information sheet.

The patient will be given adequate time to review the information sheet and ask questions. Patients may choose to give consent on the same day or take the

information home to consider. In this case patients will be given the contact details of the research nurse to arrange a follow up appointment.

A copy of the PIS and completed consent form will be uploaded onto the participant's CWS file with a record of the discussion. A copy of the consent form will be provided to the participant to keep, and a copy will be also kept in the electronic master trial file. This file will be held on a ABUHB Research and Development computer server during the course of the study.

The participant will always be given the chance to ask questions during the consent process.

For translation delegated staff will use the Wales Interpretation and Translation service. This will support the consent process, provision of information and intervention visits.

9.4. Discontinuation/Withdrawal of Participants from Study

Participants have the right to withdraw consent for participation in any aspect of the study at any time. The participants care will not be affected at any time by declining to participate or withdrawing from the study.

In this instance, participants who consent and subsequently withdraw should complete a withdrawal form with the researcher or delegated member of staff to determine and evidence the withdrawal request.

If a participant withdraws from the study, the research team will not attempt to recruit another participant. Once the target recruitment number of 20 participants has been reached, the study will be closed to recruitment.

9.5. Study Amendments

The CI will seek advice from the Sponsor prior to submission of amendments to the relevant bodies. The CI will seek approval for any substantial amendments to the protocol or other study documents from HRA/HCRW and REC (if applicable). The NHS R&D Office(s) will need to confirm capacity and capability prior to implementation. Amendments to the protocol or other study documents will not be implemented prior to these approvals being granted. Non substantial amendments should be notified to the HCRW and REC for information and may also need to be reviewed and accepted by R&D departments before they can be implemented in practice at site(s).

9.6. Definition of End of Study

Study completion will be the date of the last follow up of the last patient.

Discontinuation of the study if required will be decided upon by the Study Management Group.

10.TECHNIQUES AND TOOLS

Intervention

The Equality Health Advisors will undertake various training before implementation including a PCI Accredited Tailored Health Coaching Course. The Equality Health Advisors will access module 1 to support the coaching element of the intervention This course aims to provide tailored health coaching for Health and Social Care Professionals. All training provided will be paid through grant funding

Semi Structured Interviews

The semi structured interviews and qualitative thematic process will follow using (Braun and Clarke 2006) principles to explore both participants' experiences of participation in the intervention. This will be conducted by the researcher, preferably in person. However, there will be a video call option available to the participant. It is intended that audio recordings from the interviews will be transcribed by the researcher or may be sent to a professional transcriber, all information will remain confidential. Following transcription, the transcribed documents will be shared with the participant to ensure they agree with the transcribed information. For analysis, individual transcripts and audio recordings will be read and listened to multiple times for the researcher to fully submerge themselves in the data.

A systematic analysis to generate initial themes will be completed using computer assisted qualitative data analysis software (CAQDAS) and data will be reported in accordance with the Consolidated Criteria for Reporting Qualitative Research (COREQ) (Tong et al. 2007). A reflexive diary will be used to support separation of researcher opinion and member checks to promote credibility and confirmability. Data collection will cease once subsequent data saturation is achieved.

In addition, descriptive analysis will be made on quantitative data collected which includes validated questionnaires (Promis-10 and South Wales Social Wellbeing Scale) and case report forms, this analysis aims to understand the basic characteristics of the EQUALITY HEALTH – CVD study data, including the social economic demographics of the recruited participants.

Questionnaires

The following questionnaires will be completed at baseline and 12 weeks.

PROMIS 10 - The PROMIS 10 is a comprehensive and accessible set of tools used to measure self-reported physical, mental and social health, including symptoms, function and general perceptions of health and wellbeing.

South Wales Social Wellbeing Scale – The South Wales Social Wellbeing Scale (SWSWBS) is a tool to the quality of respondents' overall experience of social wellbeing via the external social resources they possess, their perceived ability to engage in and enjoy the social world in which they live, and, as a result, their capacity for human functioning and flourishing.

EuroQol-5D - EQ-5D is an instrument which evaluates the generic quality of life developed in Europe and widely used. The EQ-5D descriptive system is a preference-based HRQL measure with one question for each of the five dimensions that include mobility, self-care, usual activities, pain/discomfort, and anxiety/depression

The quantitative PROMS will be used in conjunction with qualitative semi structured interviews as data descriptors. The aim is to assess if the participants are willing and able to complete these measures. In addition to capturing subjective health and social wellbeing outcomes that may enhance data richness.

Physical Testing

The Equality Health Advisor will conduct a series of tests. The purpose of the physical tests is to identify participants at risk, set goals and elicit health improvement conversations, monitor progress and establish baseline measures for future testing as part of the intervention.

CE-marked/UKCA calibrated devices and equipment will be used. The Equality Health Advisor will consider the testing environment and physical limitation of participants prior to conducting a test. All tests will be safe, reproducible, validated, reliable, sensitive, acceptable to participant, and practical to undertake.

11. Protocol Compliance

Accidental protocol deviations will be adequately documented on the relevant forms and reported to the Chief Investigator.

Deviations from the protocol which are found to frequently recur are not acceptable and will require immediate action and could potentially be classified as a serious breach.

All delegated staff are ABUHB employed and adhere to ABUHB policies including the ABUHB lone worker policy. All mandatory training and DBS enhancement will be checked. In addition, a training check list will be completed and signed off before intervention implementation.

The Equality Health Advisors and Researcher (Principal Investigator) will meet (weekly/fortnightly). The Equality Health Advisors will be DBS Enhanced checked

and will receive tailored health coaching training. Further training will be undertaken and signed off using a training log prior to study implementation. A Training log is provided in the appendices. All Equality Health Advisors and delegated staff will be supported by the Principal Investigator, Chief Investigator and SOG for the duration of the study.

Furthermore, prior to study commencement the researcher will undertake training in interview techniques, in addition to qualitative and quantitative education. The researcher and delegated delivery team holds a valid Informed Consent Certification and will ensure all participants fully understand what is being asked of them in accordance with GCP guidelines.

11.1. Adverse Events and Serious Adverse Event definitions

Adverse Event (AE): Any untoward medical occurrence in a trial participant which does not necessarily have a causal relationship with this intervention. An AE can therefore be any unfavourable and unintended sign (including abnormal laboratory finding), symptom, or disease.

Serious Adverse Event (SAE): Any adverse event that:

- · Results in death
- Is life-threatening*
- Required hospitalisation or prolongation of existing hospitalisation**
- Results in persistent or significant disability or incapacity
- Consists of a congenital anomaly or birth defect
- Other medically important condition ***
- * Note: The term "life-threatening" in the definition of serious refers to an event in which the participant was at risk of death at the time of the event; it does not refer to an event which hypothetically might have caused death if it were more severe.
- ** Note: Hospitalisation is defined as an inpatient admission, regardless of the length of stay, even if the hospitalisation is a precautionary measure, for continued observation. Pre-planned hospitalisation e.g. for pre-existing conditions which have not worsened, or elective procedures does not constitute an adverse event.
- *** Note: other events that may not result in death are not life-threatening, or do not require hospitalisation may be considered as a serious adverse event when, based upon appropriate medical judgement, the event may jeopardise the participant and may require medical or surgical intervention to prevent one of the outcomes listed above.

The AEs and SAEs triggered during the study period are expected to be non-study related due the nature of this study

11.2. Reporting procedures for SAEs

Depending on the nature of the event, the reporting procedures outlined in this protocol should be followed. Any queries concerning adverse event reporting should be directed to the Chief Investigator by phone and then send the completed SAE form to the Chief Investigator within the following 24 hours.

The research team will report all related SAEs as required by their local Research and Development Office.

N.B. When setting up study reporting systems ensure no Patient/Participant Identifiable Information (PID) is e-mailed outside the University.

Contact details for reporting SAEs

Please send SAE forms to:

E-mail: [contact]

[contact] (Mon to Fri 09.00 – 17.00)

Only reports of Serious Adverse Events (SAEs) that are:

related to the study (i.e. they resulted from administration of any of the research procedures) and

unexpected (i.e. not listed in the protocol as an expected occurrence)

should be submitted to both the REC that gave a favourable opinion of the study and the Sponsor by the Chief Investigator (CI) using the Non-CTIMP safety report to REC form which is available on the HRA website https://www.hra.nhs.uk/approvals-amendments/managing-your-approval/safety-reporting/

https://www.hra.nhs.uk/documents/2466/Non_CTIMP_Safety_Report_Form_Accessi ble September 2020 AA.odt

These should be sent within 15 days of the Chief Investigator becoming aware of the event.

Unrelated and Expected SAEs do not require reporting to the Sponsor but a copy of the SAE report should be retained in the Investigator Site File for monitoring/audit unless alternative arrangements have been agreed during study set up.

The CI will send the Annual Progress Report to the main REC and to the sponsor using the HRA template.

11.3. Urgent Safety Measures and Serious Breaches of GCP

The CI and PIs may take immediate safety measures to protect research participants against any hazard to their health or safety without prior authorisation from the REC or sponsor. However, they must alert the sponsor as soon as possible of any such urgent measures by contacting the Cardiff University Research Governance Team and CI. The CI will notify the REC of the presenting issue within 3 days of the urgent measure setting out the reasons for the urgent measure and the plan for further action. If a site PI identifies the presenting issue, he or she should also inform their local R&D department.

In the event that a serious breach of GCP is suspected, this will be reported to the sponsor and REC immediately and will be investigated by the sponsor. Any corrective action required will be undertaken by the CI and REC informed. If necessary, a protocol amendment will be submitted for review.

12. STATISTICS AND ANALYSIS

12.1. Description of Statistical Methods

Questionnaires

The researcher will analyse and report response and completion rates to questionnaires, in addition to summarising descriptive variability in questionnaire outcomes.

Participant and Equality Health Advisor Interviews

Analysis of interview data will follow Braun and Clarke's thematic method and will include

- Data collection
- Data Management (using qualitative software)
- Data Analysis (familiarisation, generating codes, searching for theme, defining ad naming themes)
- Illustrative quotes will support findings

Equality Health Advisors Reflective Diaries

Analysis of reflective diaries will help understand the thoughts, feelings and experiences documented by the Equality Health Advisors over the study time period. These accounts will support findings

These points of interest are aimed to identify insights and problems that may occur before considering a full RCT.

Progression criteria

To recognise and acknowledge protocol success the following criteria will be applied using a green light system.

Criteria Progression	Green Light	Amber Light	Red Light
	Recruitment	and Attrition	
No of participants offered the intervention and declined uptake during the consent process	≤ 20%	≤ 50-74% Investigate reasons for refusal	≤ 75% Use Modify intervention Using 6 SQUID (Six-Step Quality Improvement Design)
Recruitment Rate	≥ 80% of the target number of participants recruited within the first 5 months.	50-79% of the target number recruited within the first 5 months. Implement additional recruitment strategy	49-0% of the target number recruited within the first 5 months. Reevaluate recruitment strategies and consider protocol modifications
Attrition Rate at the end of the study	25% Drop out Consider progression to RCT	Investigate reasons for dropout and implement retention strategies	75-100% Consider not proceeding with RCT funding bid submission
Follow up Completion	90-100% of participants complete the scheduled number of contact visits.	60-89% of participants complete the scheduled number of contact visits. Investigate barriers and enhance follow-up procedures.	< 75% of participants complete the scheduled number of contact visits Re-evaluate follow up strategy and consider protocol adjustments when considering future research.

Feasibility of Implementing the Intervention			
Follow up Completion	90-100% of participants complete the scheduled number of contact visits.	60-89% of participants complete the scheduled number of contact visits. Investigate barriers and enhance follow-up procedures.	< 75% of participants complete the scheduled number of contact visits Re-evaluate follow up strategy and consider protocol adjustments when considering future research.
Duration of visits	Average visit duration aligns with the planned schedule ± 10%	Average visit duration deviates from the planned schedule by 11-20%. Analyse time management and adjust visit plans if necessary.	Average visit duration deviates from the planned schedule by > 20%. Reassess visit structure and content.
Completion of Intervention Components	≥ 90% of participants complete all four components of the intervention.	75-89% completion rate. Identify and address barriers to the Labonte Model implementation	< 75% completion rate. Re-evaluate intervention design and implementation strategies.
Completion of Data Collection	≥ 95% of required data points collected	80-94% of required data points collected. Enhance data collection methods and follow-up.	80% of required data points collected. Implement corrective measures and consider protocol revisions.
Utilisation of Community and Public Service Asset	All planned community and public service assets are utilised as per individual goal plan	75-99% of planned assets are utilized. Identify reasons for underutilisation and adjust as necessary.	< 75% of planned assets are utilised. Conduct a thorough review and consider alternative assets or engagement strategies.
Participants' Acceptability and Perception			
Participant Satisfaction	≥ 80% of participants report	60-79% of participants report	< 60% of participants report

Perception of Effectiveness	high satisfaction with the intervention ≥ 80% of participants perceive the intervention as beneficial to their health and wellbeing.	high satisfaction. Investigate concerns and enhance the intervention based on feedback. 60-79% of participants perceive the intervention as beneficial. Address specific areas of concern to improve perceived effectiveness.	high satisfaction. Conduct a thorough review and consider major modifications to the intervention < 60% of participants perceive the intervention as beneficial. Re- evaluate the intervention's approach and content.
	Deliverers' Acceptal	oility and Perceived	Impact
Equality Health Advisor Satisfaction	All Equality Health Advisors report high satisfaction with the implementation process. Use of Equality Advisor Handbook	Half of the Equality Health Advisors report high satisfaction. Identify and address concerns to enhance deliverer experience. Use of Equality Advisor Handbook	Equality Health Advisors do not report high satisfaction. Conduct a detailed review and consider significant modifications to the Equality Advisor Handbook and delivery process.
Identification of Barriers and Facilitators	Comprehensive identification of key barriers and facilitators, with actionable insights.	Partial identification with some actionable insights. Further investigation needed to fully understand and address issues.	Inadequate identification of barriers and facilitators. Implement a focused review and action plan to gather necessary insights.
Perceived Impact	All Equality Health Advisors perceive the intervention as having a positive impact on participants.	Half of the Equality Health Advisors perceive a positive impact. Explore specific areas for improvement.	Equality Health Advisors do not perceive a positive impact. Reassess and potentially redesign aspects of the intervention

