8. PARTICIPANT IDENTIFICATION

8.1. Study Participants

The sample size is 20 participants. In this instance, time and resource constraints make recruiting a larger sample challenging. While 20 participants may be smaller than the typical guideline of 30 suggested by (Billingham et al. 2013) it may still provide valuable insights.

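### In the declined-uptake progression row the red cut-off is printed the wrong way round, and once it is turned, refusal above 20% and below 50% has no light

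*Protocol*

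**What the plan says.** Protocol section 12.1 sets out a traffic-light table by which the study will judge the success of its protocol. Under Recruitment and Attrition, the first row is labelled "No of participants offered the intervention and declined uptake during the consent process". Its three cells are:

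- Green: 20% or less, with no action attached.
- Amber: "≤ 50-74% Investigate reasons for refusal".
- Red: "≤ 75% Use Modify intervention Using 6 SQUID", that is, rework the intervention with a named quality-improvement method.

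The row below it, Recruitment Rate, is graded against the recruitment target. Its green cell is "≥ 80% of the target number of participants recruited within the first 5 months", amber is 50-79%, and red is "49-0% of the target number recruited within the first 5 months". Section 8.1 gives the target: "The sample size is 20 participants".

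Research question 1 in section 4 asks about feasibility and acceptability in terms of recruitment and attrition. No other section restates or corrects the declined-uptake cut-offs.

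**The concern.** Refusal is an adverse measure, so red should sit at the high end of the scale. The printed red condition is instead an upper bound, which takes in the best results and leaves out the worst. The sign in front of the amber range has no clear meaning either. Separately, no printed figure joins the end of green (20%) to the start of amber (50%).

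The study is descriptive and tests no hypothesis, so tables of this kind carry its prespecified judgements. This row is the only one that grades refusal at the point of offer. Recruitment Rate cannot stand in for it, because the target can be met at any refusal rate if enough patients are approached. If the observed rate falls where the row gives two lights or none, someone has to choose the light, and that choice may be made with the result already known.

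**Working it through.** The plan states no derived figure for this row, so there is nothing to reproduce. The check is whether the three cells cover 0-100% once each.

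**Inputs.** Green, amber and red cells of the declined-uptake row (section 12.1); target of 20 participants (section 8.1), used only for illustration.

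**Step 1: classify each whole percentage from 0 to 100.** Three readings were tried: (a) as printed, amber taken as 50-74%; (b) as printed, amber taken as 74% or less; (c) red turned to 75% or more, amber 50-74%.

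| Declined | (a) as printed, amber 50-74% | (b) as printed, amber ≤74% | (c) red ≥75% |
|---|---|---|---|
| 0-20% | green and red | green, amber and red | green |
| 21-49% | red | amber and red | **none** |
| 50-74% | amber and red | amber and red | amber |
| 75% | red | red | red |
| 76-100% | **none** | **none** | red |

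The two problems belong to different readings. On the printed sign, 21-49% does have a light (red), and the range without one is above 75%. On the corrected sign, the top of the scale is graded and the gap lies between green and amber. On a continuous scale that gap runs from just above 20% to just below 50%: 50 − 20 = 30 percentage points.

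**Step 2: put the gap into patients.** Assume 20 consents, and that everyone offered either consents or declines. With d refusals, the declined share is d / (20 + d).

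- Green requires d / (20 + d) ≤ 0.20, so d ≤ 5. Check: 5/25 = 20.0%.
- Amber begins at d / (20 + d) = 0.50, so d = 20. Check: 20/40 = 50.0%.
- Between them, d = 6 gives 6/26 = 23.1% and d = 19 gives 19/39 = 48.7%.

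All 14 counts from 6 to 19 refusals are therefore ungraded under reading (c). For example, 11 refusals give 11/31 = 35.5%.

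There is also a sliver between 74% and 75% under reading (c): 57 to 59 refusals give 57/77 = 74.0% (just above 74) to 59/79 = 74.7%. Rounding to whole percentages would remove it.

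**Step 3: compare with a complete row.** Recruitment Rate (80% or more, 50-79%, 0-49%) covers every whole percentage once. The same table therefore already contains a row built as this one should be.

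**The case against.** The strongest reply is that the red sign is an obvious slip. Refusal is the measure, amber ends at 74% and the red action is to change the intervention, so 75% or more is the only coherent meaning and nobody would call 10% refusal red. That stands, and it makes the literal contradictions unlikely to do harm in practice. It does not settle what happens between 20% and 50%.

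One could try to close that gap as well, by reading amber as everything up to 74% and letting green take precedence. But then the printed 50 has no function, and no precedence rule is stated.

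A fault in reading the PDF is possible in principle. It is unlikely, because the opposite sign is preserved in the next row ("≥ 80% of the target number of participants recruited within the first 5 months"), and a misread sign would not explain the gap in the figures.

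It is also fair to say that the practical effect is limited. Section 9.2 already has reasons for non-participation sought and logged at any refusal rate. Under section 6, the Study Operational Group receives screening-log summaries and can inform amendments. These arrangements supply the information, but they do not assign a light.

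Three stronger readings are tempting and are not supported:

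- **That all the faults apply together.** They do not. Low refusal being red, and very high refusal having no light, need the printed sign; the gap at 21-49% needs the corrected one.
- **That this row decides whether a full trial goes ahead.** Its actions are to investigate refusals or modify the intervention. In this table, the decision about proceeding to an RCT is attached to the attrition row.
- **That red was meant to start at 50%.** The table prints 50-74% as amber.

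**Conclusion.** The row is wrong as written. The red sign is reversed, and correcting it leaves refusal above 20% and below 50%, 30 percentage points, without a light. With 20 consents that is 6 to 19 refusals, or 23.1% to 48.7%.

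The patient counts rest on two assumptions: that exactly 20 consent, and that everyone offered either consents or declines. The protocol gives no expected refusal rate or number to be approached, so how likely a result in the gap is cannot be judged from the document. The label speaks of a number while the cells are percentages, and no denominator is stated.

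This is a drafting error in a stated threshold, not detail that could be left to an analysis plan. It bears on research question 1, but it affects no estimate and no stopping decision. That the light would be chosen after the data are seen is a risk, not something the protocol plans.

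**What to change.** Restate the declined-uptake row so that every value from 0 to 100% has exactly one light, keeping the outer figures already printed:

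- Green: 20% or less.
- Amber: above 20% and below 75%.
- Red: 75% or more.

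This removes the stray sign before the amber range and closes the sliver between 74% and 75%. If the team would rather give part of the range above 20% and below 50% to green, it should say so and print the boundary; that choice is the team's.

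Reword the label as a percentage and name the denominator: all patients offered the intervention. Confirm that the screening logs record who was offered as well as who declined.

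Make the change before refusal data are reviewed. If they have already been reviewed, date the change and declare that in the report.

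The cost is one table row, taken through the amendment route in section 9.5. If the logs already record offers, no new data collection is needed.
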